Assessment of lytic bone disease	х	As clinically indicated to document response or progression.	x	-	• The same methodology used during screening should be used throughout the study for comparison purposes
Extramedullary soft tissue plasmacytomas (in patients with history of extramedullary soft tissue plasmacytoma, physical or radiologic examination to be done as applicable)	x	As applicable, by physical exam every 4 weeks, or by radiologic exam every 12 weeks; to be conducted within 14 days before a scheduled visit.	-	-	 Not required during screening if performed as part of standard of care within 30 days before screening.
Other malignancy (other primary or recurrent malignancy diagnosed after initiation of study treatment)	-	x	x	Every 6 months	Data on other malignancy, survival status, date of PD on next line of therapy, next line of therapy along with start/stop date should be entered in eCRF at each study visit, as applicable, during the maintenance treatment and, every 6 months (24 weeks) during follow- up phase.
Next-line therapy and start/stop date	-	Х	Х		-
Survival	-	Х	X		-
Date of PD on next-line therapy	-	Х	X		-
ONGOING PATIENT REVIEW					
Adverse events	Continuous	from the time of signing of the days) after last dose of	Note: If a patient is unable to return to the site for the EOT Visit, then he/she should be contacted to collect adverse events and		

	STUDY PHASES/VISITS ^a					
PROCEDURE	Screening	Maintenance (Cycles 1 – 36)	ЕОТ	Follow-up (from the date of last study treatment until the end of study)	Notes	
Concomitant medications					concomitant therapies that occur within 30 days (± 7 days) after the last dose of study treatment(s).	
					See Section 8 and Section 11.1 for detailed instructions regarding concomitant medication use and reporting adverse events, respectively.	
Key: β -hCG = beta hormone human chorion	nic gonadotropi	n; ALT = alanine aminotransf	erase; an	tiHBc = antibody to hepatitis B core	e antigen; antiHBs = antibody to hepatitis B surface	
antigen; ASCT = autologous stem cell	transplant; AS	T = aspartate aminotransferase	; BUN =	blood urea nitrogen; C = cycle (cycl	le number); COPD = chronic obstructive pulmonary	
disease; CR = complete response; CT	= computed tor	nography; D = day (day numb	er of cyc	le); ECG = electrocardiogram; ECO	G = Eastern Cooperative Oncology Group; eCRF =	

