10.2.2. Withdrawal From the Study

A patient will be withdrawn from the study for any of the following reasons:

- Lost to follow-up
- Withdrawal of consent for study participation
- Death
- Sponsor terminates the study

If a patient is lost to follow-up, every reasonable effort must be made by the study-site personnel to contact the patient and determine the reason for discontinuation/withdrawal. The measures taken to follow-up must be documented.

When a patient withdraws consent before completing the study, the reason for withdrawal is to be documented in the eCRF and in the source document. Study treatment assigned to the withdrawn patient may not be assigned to another patient. Patients who withdraw will not be replaced. If a patient discontinues study treatment and withdraws from the study before the EOT Phase, EOT assessments should be obtained. If the reason for withdrawal from the study is withdrawal of consent, then no additional assessments are allowed.

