16.2.3. Informed Consent

Each patient (or a legally acceptable representative) must give written consent according to local requirements after the nature of the study has been fully explained. The ICF(s) must be signed before performance of any study-related activity. The ICF(s) that is/are used must be approved by both the sponsor and by the reviewing IRB and be in a language that the patient can read and understand. The informed consent should be in accordance with principles that originated in the Declaration of Helsinki, current ICH and GCP guidelines, applicable regulatory requirements, and sponsor policy.

Before enrollment in the study, the investigator or an authorized member of the study-site personnel must explain to potential patients or their legally acceptable representatives the aims, methods, reasonably anticipated benefits, potential hazards of the study, and any discomfort participation in the study may entail. Patients will be informed that their participation is voluntary and that they may withdraw consent to participate at any time. They will be informed that choosing not to participate will not affect the care the patient will receive for the treatment of his or her disease. Patients will be told that alternative treatments are available if they refuse to take part and that such refusal will not prejudice future treatment. Finally, they will be told that the investigator will maintain a patient identification register for the purposes of long-term follow up if needed and that their records may be accessed by health authorities and authorized sponsor personnel without violating the confidentiality of the patient, to the extent permitted by the applicable law(s) or regulations. By signing the ICF, the patient or legally acceptable representative is authorizing such access, which includes permission to obtain information about his or her survival status. It also denotes that the patient agrees to allow his or her study physician to recontact the patient for the purpose of obtaining consent for additional safety evaluations and subsequent disease-related treatments, if needed. The physician may also recontact the patient for the purpose of obtaining consent to collect information about his or her survival status.

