5.4.1. Definition

MRD by NGS are evaluated post-baseline at the end of 12, 18, 24, and 36 months after the start of study treatment(s). The overall MRD negativity (10^{-5}) conversion rate at any time after randomization is defined as the rate of MRD converted from positive at baseline to negativity at the threshold 10^{-5} achieved at any time after randomization.

In addition, MRD negativity (10^{-5}) conversion rate at 12, 18, 24 and 36-months landmark time with +/- 2 months window, as well as accumulative rate up to these timepoints will be summarized. MRD negativity (10^{-5}) CR conversion rates for FAS patients, and MRD negativity (10^{-5}) conversion rates for those achieved CR or better response per computerized algorithm will be summarized in a similar manner.

Durable MRD (≥ 1 year) negativity rate, defined as the proportion of subjects who have achieved MRD negative status (at 10⁻⁵) in 2 bone marrow aspirate examinations that are a minimum of 1 year apart, without any examination showing MRD positive status in between assessments. Subjects who have achieved MRD negative status on or after PD or switch to subsequent antimyeloma therapy before PD, will not be considered MRD negative. Subjects with missing or unevaluable MRD status will be considered as MRD positive.

Similar analysis will be performed for durable MRD (≥6 months) negativity rate.

OS, measured from the date of randomization to the date of the subject's death due to any cause. Subjects who died after consent withdrawal will be considered as having an OS event. Subjects who are lost to follow-up will be censored at the time of lost to follow-up. If the patient is alive and vital status is unknown, then the patient's data will be censored at the date the patient was last known to be alive determined by the maximum collection/assessment date from among selected data domains within the clinical database.

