PFS2 is defined as the time from randomization to progression on next line of therapy or death, whichever comes first. Disease progression on the next line of treatment will be based on investigator assessment. Any deaths are considered as PFS2 events. Subjects who start next line of therapy without disease progression on study treatment will be censored at the last disease assessment before starting next line of therapy. For subjects who start next line of therapy after progression on study treatment, are still alive and not yet progress on next line of therapy or progressed on or after a 2nd line of next therapy, they will be censored on minimum of the last date of follow-up and start date of 2nd line of next therapy minus 1. Subjects without any post-baseline follow-up will be censored at the randomization. Time to subsequent antimyeloma therapy is defined as the time from randomization to the start of subsequent antimyeloma treatment. Death due to PD without start of subsequent therapy will be considered as event. Subjects who withdrew consent to study or are lost to follow, or die due to causes other than disease progression will be censored at the date of death or the last date known to be alive.

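### Time to subsequent therapy has no censoring limit at consent withdrawal, so a withdrawn patient with a later alive or non-progression death date is credited with therapy-free time that nobody observed

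*SAP*

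**What the plan says.** SAP 5.4.1 defines the endpoint: "Time to subsequent antimyeloma therapy is defined as the time from randomization to the start of subsequent antimyeloma treatment". A death from progression with no subsequent therapy also counts as an event. The censoring sentence names three groups, "Subjects who withdrew consent to study or are lost to follow, or die due to causes other than disease progression", and says that they "will be censored at the date of death or the last date known to be alive". It sets no limit at the date of withdrawal, or at the last contact at which therapy was asked about. Under SAP 5.4.2 the endpoint is analysed like PFS (Kaplan-Meier, stratified log-rank, stratified Cox).

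Three other statements decide what the rule does in practice:

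- Protocol 10.2.2: "If the reason for withdrawal from the study is withdrawal of consent, then no additional assessments are allowed".
- Protocol 16.2.3: signing the consent form authorises access to records, "which includes permission to obtain information about his or her survival status".
- SAP 5.4.1, under OS: "Subjects who died after consent withdrawal will be considered as having an OS event". The OS paragraph also gives the only definition of the alive date, the date the patient was "last known to be alive determined by the maximum collection/assessment date from among selected data domains within the clinical database".

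For PFS, by contrast, SAP 5.3.1 (Table 4) censors withdrawn and lost patients at their last disease assessment before leaving. Its footnote censors patients who die after withdrawing at the withdrawal date.

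**The concern.** A censoring date should be the last date on which the event would have been seen had it happened. After consent is withdrawn, next-line therapy is no longer collected, but a death or an alive date may still reach the database. The rule then carries the patient as at risk and therapy-free from withdrawal up to that later date. A therapy started in between is not recorded.

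The time at risk is inflated, so the therapy-start rate is understated and the Kaplan-Meier curve is too favourable in any arm with such patients. If the arms differ in how many patients withdraw, or in how often vital status is learned afterwards, the hazard ratio is distorted too. Such a difference is possible in an open-label trial.

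**Working it through.** **Texts side by side.**

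1. Therapy status after consent withdrawal: no planned source (Protocol 10.2.2).
2. Vital status after consent withdrawal: deaths are used (SAP 5.4.1, OS), and survival status may be obtained (Protocol 16.2.3).
3. Censoring date for this endpoint: driven by item 2, although the event depends on item 1.
4. Patients lost to follow-up: Protocol Time and Events Schedule, Part 1, collects "Data on other malignancy, survival status, date of PD on next line of therapy, next line of therapy along with start/stop date" together, at study visits and then every 6 months. Both normally stop at the same contact, so a gap needs a later date from another source.

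**Size.** The documents give no sample size, event count or power for this endpoint, so there is no figure of the plan's to reproduce. All inputs below are assumptions. The medians (R 60 months; DR 60 or 120), the accrual period (12 months) and the follow-up (36 months after the last patient) are borrowed from the PFS planning in SAP 1.4.

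Notation:
- λ = ln 2 / median
- F = follow-up, uniform on 36 to 48 months (mean 42)
- L = time of withdrawal
- w = share who withdraw
- v = share of those whose vital status is known to study end
- A = E[(1 − e^(−λF))/λ], mean observed time of a patient who stays
- B = E[(1 − e^(−λL))/λ], mean observed time of one who withdraws
- C = E[(F − L)e^(−λL)], mean unobserved time credited per withdrawn patient with v = 1

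The correct person-time is P = (1 − w)A + wB, and the SAP rule uses P + wvC. Recorded events are the same under both, so the rate under the SAP rule divided by the correct rate is P / (P + wvC).

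Check on the borrowed inputs: expected events are 107·λ·A per arm. For R, 107 × 0.01155 × 33.23 = 41.1. For DR at 120 months, 107 × 0.005776 × 37.27 = 23.0. The total is 64.1, against 64 stated for PFS.

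*Withdrawal uniform over the first 24 months, median 60:* A = 33.23, B = 10.96, C = 26.68.
- w = 10%, v = 1: P = 0.9 × 33.23 + 0.1 × 10.96 = 31.01; credited time 2.67; 31.01/33.68 = 0.921, or 7.9% too low.
- w = 10%, v = 0.1: 31.01/31.27 = 0.991, or 0.9% too low.
- v = 0: no effect.

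*Withdrawal uniform over all follow-up, median 60:* B = C = 17.96.
- w = 10%, v = 1: P = 31.71; 31.71/33.50 = 0.946, or 5.4% too low.
- w = 10%, v = 0.1: 0.6% too low.

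*Hazard ratio, first 24 months, v = 1.* The rate factors for R (median 60) are 0.960 at w = 5% and 0.882 at w = 15%. For DR at median 120 (A = 37.27, B = 11.46, C = 28.27) they are 0.962 and 0.887.

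| Withdrawal, R vs DR | True HR 1.00 becomes | True HR 0.50 becomes |
|---|---|---|
| 15% vs 5% | 0.960/0.882 = 1.09 | 0.5 × 0.962/0.882 = 0.545 |
| 5% vs 15% | 0.882/0.960 = 0.92 | 0.5 × 0.887/0.960 = 0.46 |
| 10% vs 10% | 1.00 | 0.50 |

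With withdrawal spread over all follow-up, 15% vs 5% gives 1.06 and 0.53. These are ratios of events per person-time, used as a stand-in for the Cox estimate. Deaths are not modelled.

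**The case against.** Four arguments limit the point.

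**Lost patients.** Because therapy and survival are asked about at the same contacts, a lost patient's last alive date will usually be the last date on which therapy status was known. This stands. A reader might infer that the rule misfires equally for withdrawn and lost patients; the collection schedule does not support that.

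**Later vital status may be scarce.** The alive date comes from the clinical database, and assessments stop at withdrawal. Protocol 16.2.3 also speaks of recontacting patients to seek consent for survival information, which suggests that some later data may need fresh consent. For a withdrawn patient who is alive, the date may therefore often fall near withdrawal. This limits how often the problem occurs but does not remove it, since the SAP expressly uses deaths after withdrawal.

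**Some events are still captured.** A withdrawn patient who later dies of progression can count as an event, though late, and with the condition of no prior therapy unverifiable. This is a partial offset, and the calculation above omits it.

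**Low stakes.** The endpoint was added in SAP version 2.0, and SAP 5.1.1 treats it as exploratory, without multiplicity adjustment. This stands.

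**Conclusion.** The point holds as a gap in one censoring definition. It is clear for patients who withdraw consent and have a later alive date or a later death not due to progression. It is conditional for patients lost to follow-up. The SAP's own PFS rule shows that the authors apply the right principle elsewhere.

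With 10% withdrawing in each arm, the therapy-start rate is about 5% to 8% too low if vital status is known to study end for all of them, about 1% or less if for a tenth, and unaffected if for none. With balanced withdrawal and ascertainment the hazard ratio is essentially unchanged. With 15% vs 5%, full vital status and early withdrawal, 1.00 moves to 1.09 or 0.92 and 0.50 to about 0.545 or 0.46, depending on which arm loses more. The shift is smaller if withdrawal is later or vital status is known for fewer.

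A reader might infer that the reported hazard ratio will be biased, or biased in favour of daratumumab. The documents do not support either: they give no withdrawal rate, no imbalance and no rate of later ascertainment. The primary endpoint, PFS and alpha control are not affected. This is a worthwhile clarification, not a threat to the trial's conclusions.

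**What to change.** Amend the censoring sentence in SAP 5.4.1 along these lines:

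- Patients who withdraw consent or are lost to follow-up, with no therapy start or other event recorded by then, are censored at the last date on which subsequent therapy was documented as not started, on or before withdrawal or last contact. This applies also if they die afterwards, in keeping with the PFS treatment of deaths after withdrawal in Table 4.
- Deaths not due to progression are censored at the date of death, and deaths from progression without subsequent therapy count as events, only for patients still in follow-up when they die.

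The second sentence is needed so that the two rules do not collide for a patient who withdraws and later dies. The cost is one or two sentences, one change to the derivation, and the loss of a few late progression-death events after withdrawal.

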5.4.2. Analysis Methods

The analysis of the overall MRD (10^{-5}) conversion rate at any time after randomization, durable MRD negativity rate, the CR or better rate, and sCR rate will be performed similarly to that for the primary endpoint on the FAS, as described in Section 5.2.3. Similarly, for thresholds 10^{-4} and 10^{-6} , the overall MRD negativity rate at any time after randomization will be analyzed similarly as for the threshold 10^{-5} .

The time-to-event variables (ie., OS, duration of CR, PFS2 and time to subsequent antimyeloma therapy) will be performed using the approach for PFS, as described in Section 5.3.2.

Time to the first response of CR or better will be summarized using descriptive statistics for those who reached CR or better response.

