11.3.2. Secondary Endpoints and Analysis

11.3.2.1. Progression-free Survival, Overall Survival, and Minimal Residual Disease

Time-to-event secondary endpoints including PFS and OS will be analyzed through a stratified log-rank test for the comparison of the distribution between the 2 treatment groups. The Kaplan-Meier method will be used to estimate the distribution for each treatment. The treatment effect (HR) and its 2-sided 95% CIs are to be estimated using a stratified Cox regression model

with treatment as the sole explanatory variable stratified by baseline cytogenetic risk (high versus standard/unknown).

The overall MRD negativity rate at any time after randomization and MRD durability will be analyzed.

The binary secondary endpoints including rate of CR and sCR will be analyzed similarly to MRD negativity rate.

A descriptive summary for duration of response will be provided. No statistical comparison will be made.

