5. EFFICACY

5.1. Analysis Specifications

5.1.1. Level of Significance

All statistical hypothesis tests and 95% confidence intervals presented will be 2-sided.

The primary hypothesis is to be tested at the 0.05 significance level (overall).

If the primary endpoint of the MRD negativity (10^{-5}) conversion rate from baseline to 12 months after initiation of maintenance treatment is statistically significant, the key secondary endpoint PFS will be sequentially tested with an overall two-sided alpha of 0.05, by utilizing a hierarchical testing approach as proposed by Tang and Geller (1999)³ that strongly controls Type I error rate.

One interim analysis on the key secondary endpoint, PFS, using the Obrien-Fleming alpha spending function is planned at the time of primary endpoint analysis.

Analyses on all other efficacy endpoints are exploratory and will be tested at 2-sided 0.05 significant level without multiplicity adjustment.

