5.3.2. Analysis Methods

Analysis of PFS will be based on the FAS. The Kaplan-Meier method will be used to estimate the distribution of overall PFS for each treatment group. The median PFS with 95% CI will be provided. In addition, the number and percentage of subjects who had a PFS event or were censored will be reported. The reasons for PFS censoring will be summarized accordingly. The Kaplan-Meier PFS curve will also be plotted by treatment group.

The treatment comparison of the distribution of overall PFS will be based on a stratified log-rank test. The p-value from a stratified log-rank test will be reported. Hazard ratio and its 95% confidence interval will be estimated based on a stratified Cox's regression model with treatment

as the sole explanatory variable. Stratification factor used in the analyses include baseline cytogenetic risk (high risk versus standard/unknown risk) as used for randomization of the study.

In addition, PFS rate with 95% CI will be estimated at various time points by Kaplan-Meier method for each treatment group.

To evaluate the robustness of PFS analysis, the following sensitivity and supplementary analyses may be performed in a similar manner as described above:

Sensitivity

- Unstratified analysis of PFS by using unstratified log-rank test and unstratified Cox's regression model
- Progressive disease based on investigator assessment according to the IMWG response criteria
- Not censoring for death or disease progression after 2 or more missing consecutive disease evaluations: For any disease progression identified by the computer algorithm or death, if there are 2 or more consecutive missing scheduled disease evaluations between the event date and the latest date of scheduled disease evaluation (includes serum M-protein, urine M-protein, and serum FLC only) immediately preceding the event, this event will be considered as a PFS event in the analysis

Supplementary

- Not censor the events after the start of subsequent antimyeloma therapies; Progression or death occurred after the start of subsequent anti-myeloma therapies will NOT be censored at the last disease assessment before the start of subsequent therapies. If there is no confirmed progressive disease, the subjects will be censored at the last disease assessment before subjects are lost to follow-up or withdrawal of consent to study

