Response rates by IMWG 2016 criteria including CR or better rate and sCR rate, defined as the proportion of subjects who achieve the respective responses prior to the first subsequent antimyeloma therapy per computer algorithm in accordance with the IMWG criteria, during or after the study treatment. All subjects are assumed to be VGPR at baseline to enter the study per inclusion criteria. Subgroup analysis will be performed for CR or better rate per computer algorithm with forest plot provided. In addition, responses per investigator assessment by IMWG 2016 criteria will be summarized. Shift tables will be provided to summarize the best responses from baseline vs. post-baseline for each treatment group.

Duration of CR, calculated from the date of initial documentation of a response of CR or sCR at or after randomization to the date of first documented evidence of PD (as defined in the IMWG criteria), or death due to PD, whichever occurs first, for subjects who have CR or better as their best response. Subjects who have not progressed or who die due to causes other than disease progression will be censored at the last disease evaluation before the start of subsequent antimyeloma therapy. Subjects who achieved CR or sCR prior to randomization will use randomization date as their starting time of CR or sCR for calculating duration of CR.

Time to the first response of CR or better is defined as the time between randomization and the first efficacy evaluation at which the subjects meet all criteria for CR or better based on computerized algorithm, according to IMWG response criteria. For subjects who achieved CR or sCR prior to randomization, time to CR or better will be set as 0 day.

In addition to protocol specified other secondary efficacy endpoints, progression-free survival on next line of therapy (PFS2) and time to subsequent therapy will be evaluated.

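### SAP 5.4.2 applies the PFS log-rank and Cox comparison to duration of CR, a responders-only endpoint that the protocol says will be described but not compared

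*SAP*

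**What the plan says.** SAP 5.4.2 assigns the method. Its list of time-to-event variables opens with OS and continues "duration of CR, PFS2 and time to subsequent antimyeloma therapy) will be performed using the approach for PFS", with a pointer to Section 5.3.2. That section contains more than Kaplan-Meier estimation. It states that "The treatment comparison of the distribution of overall PFS will be based on a stratified log-rank test", with the p-value reported, and that the hazard ratio and its 95% confidence interval are "estimated based on a stratified Cox's regression model with treatment" as the only explanatory variable.

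The populations differ. For PFS, "Analysis of PFS will be based on the FAS". SAP 5.4.1 defines duration of CR only "for subjects who have CR or better as their best response". It adds that subjects who reached CR or sCR before randomisation start the clock on the randomisation date.

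Protocol 11.3.2.1 says that duration of response gets a descriptive summary, followed by "No statistical comparison will be made". The protocol synopsis says the same. SAP 5.1.1 sets the status of everything outside MRD conversion and PFS: "Analyses on all other efficacy endpoints are exploratory and will be tested at 2-sided 0.05 significant level without multiplicity adjustment".

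**The concern.** There are two problems.

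First, the SAP would produce a p-value and a hazard ratio that the protocol says will not be produced. Nothing in the SAP exempts duration of CR, and its version history does not record the change.

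Second, the protocol's restriction has a statistical reason. Whether a subject reaches CR after randomisation is itself an efficacy outcome compared between the arms. If the combination brings additional patients into CR, the two groups of responders need not be alike in prognosis. A hazard ratio between them then mixes that difference in composition with any real difference in durability. At stake is how a named secondary endpoint is read: a nominally significant result, in either direction, could be taken as evidence about durability when it reflects who entered the comparison.

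**Working it through.** **Step 1: the provisions side by side.**

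| Question | Protocol 11.3.2.1 and synopsis | SAP 5.4.2, 5.3.2 and 5.4.1 |
|---|---|---|
| Endpoint | Duration of response; the only one defined (Table 1) is duration of CR | Duration of CR, by name |
| Summary | Descriptive | Kaplan-Meier, as for PFS |
| Between-arm test | None | Stratified log-rank |
| Effect estimate | None | Stratified Cox hazard ratio with 95% CI |
| Endpoints named for log-rank | PFS and OS | OS, duration of CR, PFS2, time to subsequent therapy |

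The sentence after the list in SAP 5.4.2 makes time to first CR or better descriptive only. The SAP therefore says so when it wants no comparison, and it does not say so for duration of CR.

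**Step 2: who is compared.** Entry requires VGPR or better, so some subjects may already be in CR at randomisation. Their CR status is fixed beforehand, and a comparison among them alone would keep the protection of randomisation. Subjects who convert later do not form such a group. The planned analysis pools the two. The documents do not give the share of each.

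**Step 3: how large the distortion could be.** The plan gives no figure for duration of CR, so there is nothing to reproduce. The illustration takes 107 per arm from the sample-size section. All other inputs are assumptions.

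- Patients are of three types: CR on either arm (proportion p_R, hazard λ = ln 2 / median), CR only on the combination (p_D − p_R, hazard k·λ), and never CR.
- Treatment changes no patient's event time. Times are exponential, the clock starts at randomisation, and an unstratified log-rank test or Cox model is applied to responders only.
- Setting A: CR 40% v 60%, median 60 months, follow-up 36 to 48 months (1 year of accrual plus 36 months after the last randomisation). 4,000 trials per cell.
- Setting B: CR 50% v 75%, otherwise as A.
- Setting C: CR 50% v 70%, median 72 months, follow-up 24 to 48 months (4,000 and 1,500 trials per cell). It was repeated at 36 to 48 months (1,500 trials) for k = 1, 1.2, 1.5 and 2.4.

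In setting C the expected responders are 107 × 0.50 = 53.5 on lenalidomide and 107 × 0.70 = 74.9 on the combination, of whom 107 × 0.20 = 21.4 are extra. The multiple k is 72 divided by the extra responders' median: 72/60 = 1.2, 72/48 = 1.5, 72/36 = 2, 72/30 = 2.4 and 72/24 = 3.

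Rejection rate at a nominal two-sided 5%:

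| k | A | B | C |
|---|---|---|---|
| 1 | 4.9% | 5.7% | 4.5 to 5.2% |
| 1.2 | not run | not run | 4.3 to 4.7% |
| 1.5 | 6.9% | 6.7% | 6.0 to 6.3% |
| 2 | 12.6% | 14.5% | 10.6% |
| 2.4 | not run | not run | 13.7 to 14.7% |
| 3 | 26.8% | 30.3% | 20.6% |

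The simulation standard error is √(p(1−p)/N): √(0.05 × 0.95/4,000) = 0.3 points near 5%, and √(0.14 × 0.86/1,500) = 0.9 points near 14%.

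In setting C (24 to 48 months) the geometric-mean hazard ratio, combination over lenalidomide, is 1.00, 1.14, 1.27, 1.34 and 1.46 for k = 1, 1.5, 2, 2.4 and 3. The geometric mean is used because the arithmetic mean of estimated hazard ratios is pulled upward when events are few: it is 1.06 to 1.08 even when k = 1.

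**The case against.** Four points can fairly be made for leaving the plan alone.

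- **Wording.** The protocol speaks of duration of response, not duration of CR, and its general sentence on time-to-event endpoints could be stretched to cover the latter. The reading used here is an inference. It is a firm one: no other duration-of-response endpoint is defined, and the specific exclusion sits in the same section as the general sentence.
- **Size.** Every effect input in the illustration is assumed. The distortion is absent if the added responders resemble the others, and small up to 1.5 times their hazard. This stands. A reader might infer from the larger cells that the analysis will be materially biased against the combination, or that bias the other way is just as likely. The documents support neither: they contain nothing on the prognosis of the additional responders.
- **Selection.** A reader might infer that every subject in the analysis is selected after randomisation. SAP 5.4.1 shows otherwise, since those in CR beforehand are a baseline-defined group. This narrows the problem to new converters, but pooling them with the others still breaks the randomised comparison.
- **Status.** A reader might infer that error control for the trial is compromised. It is not. SAP 5.1.1 puts only MRD conversion and PFS in the hierarchy, and unselected results for CR rate, OS and PFS2 will be reported alongside. The exploratory label does not remove the conflict with the protocol, nor does it make the hazard ratio interpretable.

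**Conclusion.** The point holds as a protocol-SAP conflict on one exploratory secondary endpoint, and the protocol has the sounder position. The SAP calls for a log-rank p-value and a Cox hazard ratio in a group partly selected by a post-randomisation outcome.

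The size of any bias is unknown. With 20 to 25 percentage points more CR on the combination and no effect on any patient's duration, the assumed scenarios run from no inflation to a rejection rate of about 30%. The result depends almost wholly on how much worse the extra responders are. The illustration is unstratified and starts the clock at randomisation for everyone, whereas the plan stratifies by cytogenetic risk and starts later for new converters. It shows mechanism and range, and is not evidence about this trial.

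The case for changing the SAP rests on the conflict and the lost protection of randomisation, not on any one simulated figure. It should be corrected. It does not bear on the primary or PFS conclusions.

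**What to change.** In SAP 5.4.2, delete duration of CR from the variables analysed by Section 5.3.2. Add a sentence saying that it will be summarised by arm with Kaplan-Meier curves and medians among subjects with CR or better, with no log-rank test and no hazard ratio, in line with protocol 11.3.2.1.

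The cost is one line of SAP text and one exploratory p-value and hazard ratio fewer. Data collection, sample size and alpha do not change. A comparative in-CR measure on the full analysis set would be an optional addition and is not needed to resolve the conflict.
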